8.7.4. Aim 3B

To estimate long-term healthcare resource utilization and costs associated with COVID-19 by vaccination status, age, and site of care.

Exposure: Persons will be considered a COVID-19 patient if they experienced a COVID-19-related encounter, regardless of setting (cases). COVID-19 patients (cases) will be matched to 4 patients

without a COVID-19 diagnosis (controls) using the matched index date. Controls may or may not have had health care encounters during the study period. Cases and controls will be matched based on age, sex, insurance type, previous Charlson Comorbidity Index (CCI), number of previous hospitalizations, and follow-up time. The CCI and number of hospitalizations were calculated by using diagnoses during pre-index. For stratification/subgroup analyses, adult persons will be considered vaccinated if they received the BA.4.5 dose 14 or more days prior to index, persons will be considered unvaccinated if they had not received any COVID-19 vaccination doses. Children will be considered vaccinated if they received the any COVID-19 vaccination dose 14 or more days prior to index and will be considered unvaccinated if they had not received any COVID-19 vaccination doses.

Study Period (data including pre-index and follow-up): 01 June 2021 – 31 August 2023

Patient identification (index) window: June 2022 - November 2022

Follow-up time: starting 30 days after first COVID-19 diagnosis (index date) with follow-ups of 1 month, 3 months, 6 month, and 9 months.

Outcomes of interest: Similar to those in Pike et al, 2023

[figure not shown]
- All-cause direct healthcare costs (medical and pharmacy)
- All-cause Healthcare resource utilization
- COVID-19-related hospitalization (for cases only)

Statistical Methods: All analyses will be pooled across California and Louisiana, and stratified by state. Descriptive statistics will be used to summarize patient characteristics, with mean (standard deviation) or median (25th percentile – 75th percentile) for continuous variables and counts (percentages) for categorical variables. A regression model will be developed that adjusts for age, sex, and baseline comorbidities. We will stratify outcomes by vaccination status, healthcare cost (medical and pharmacy), and sites of care (inpatient, outpatient, etc.).

8.7.5. Aim 4

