 - a. Or, have a location other than California or Louisiana in their HealthVerity claims enrollment file record but have one or more records in the California or Louisiana Immunization Registry. Examples include people who previously lived in Texas but moved to California/Louisiana and received a vaccine, or residents of other states who crossed state lines to receive a vaccine in California or Louisiana.

Matched Control Patients:

- 1. Control patients will be exact-matched up to 4:1 to COVID-19 patients using the following matching criteria:
 - a. Control patients will be assigned a random date between 01 June 2022 and 30 November 2022 as the index date. The control patients' index date will be further required to be within the \pm 14 days of the index date of their corresponding matched COVID-19 patients.
 - i. Have continuous medical and prescription insurance coverage between June 1, 2022 and November 30, 2022
 - ii. To ensure that the follow-up period of control patients will not be post-COVID-19, control patients are required to have no COVID-19 diagnoses in any position in any inpatient or outpatient claims prior to 30 November 2022.

- Control patients are allowed to have a COVID-19 diagnosis after 30 November 2022 as long as all other patient matching criteria are met. In such cases, the follow-up period of these control patients will be censored at the date of the first inpatient or outpatient claim with a COVID-19 diagnosis in any position.
- iii. Control patients will have similar continuous insurance enrollment criteria as the COVID-19 patients, described as below:
 - Similar to their matched adult and pediatric COVID-19
 patient counterparts, control patients will be required to have
 12 and 6 months of continuous baseline enrollment,
 respectively.
 - Control patients will be required to have continuous medical and prescription insurance coverage for at least 1 month after the index date (follow-up period).
- Control patients will be matched 4:1 without replacement to COVID-19 patients using the following criteria (exact match unless otherwise specified).
 - i. Index date within ± 14 days of the index date of the COVID-19 patient
 - ii. Age
 - Sample size permitting, an exact match of age will be used.
 If not, matched patients will be required to be within the same age group (see Table 1) AND have an age gap of no more than 2 years (control patient age = COVID-19 patient age ± 2 years).
 - iii. Gender
 - iv. State

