All Pharmacy Claims - Follow-up (Yes/No)	Outcome	HealthVerity	Proportions of patients with any pharmacy claims during the follow-up period. Reported as counts and percentages.
Number of All Pharmacy Claims – Follow-up	Outcome	HealthVerity	Number of pharmacy claims during the follow-up period. Reported as min, max, median (Q1-Q3) and mean (SD).
Total Costs of All Pharmacy Claims - Follow-up	Outcome	HealthVerity	Sum of the costs of all pharmacy claims during the follow-up period. Reported as min, max, median (Q1-Q3) and mean (SD).
Total Costs of All Healthcare Claims - Follow-up	Outcome	HealthVerity	Sum of the costs of all healthcare, including inpatient, outpatient and pharmacy claims during the follow-up period. Reported as min, max, median (Q1-Q3) and mean (SD).
Number of COVID-19 Outpatient Visits -	Outcome	HealthVerity	Number of COVID-19 related outpatient visits during the follow-up period. COVID-19-related

SAP version 1.0, 30 May 2024

Variable	Role	Data source	Operational definition
Follow-up			outpatient visits are identified by an outpatient visit diagnosis of COVID-19 in any position. Reported as min, max, median (Q1-Q3) and mean (SD). The same measurements will be reported for the following sub-groups: office visits, emergency department, urgent care claims, others.
Total Costs of COVID- 19 Outpatient Visits - Follow-up	Outcome	HealthVerity	Sum of the costs of COVID-19 related outpatient visits during the follow-up period. COVID-19-related outpatient visits are identified by an outpatient visit diagnosis of COVID-19 in any position. Reported as min, max, median (Q1-Q3) and mean (SD). The same measurements will be reported for the following sub-groups: office visits, emergency department, urgent care claims, others.
Number of COVID-19 Hospitalization - Follow-up	Outcome	HealthVerity	COVID-19-related hospitalizations during the follow-up period. COVID-19 hospitalizations are identified by a hospital discharge diagnosis of COVID-19 in any position. Reported as min, max, median (Q1-Q3) and mean (SD).
Total LOS of COVID-19 Hospitalization - Follow-up	Outcome	HealthVerity	Sum of the LOS of COVID-19-related hospitalizations during the follow-up period. Any overlapping inpatient days will only be counted once. Reported as min, max, median (Q1-Q3) and mean (SD).

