Total Costs of COVID- 19 Hospitalization - Follow-up	Outcome	HealthVerity	Sum of the costs of COVID-19-related hospitalizations during the follow-up period. Reported as min, max, median (Q1-Q3) and mean (SD).
COVID-19 Hospitalization Status (Yes/No) - Follow-up	Outcome	HealthVerity	Proportions of patients with or without COVID-19- related hospitalizations during the follow-up period. Reported as counts and percentages.
Total Costs of COVID- 19 Medical Claims - Follow-up	Outcome	HealthVerity	Sum of the costs of all COVID-19-related medical claims, including inpatient and outpatient medical claims during the follow-up period. Reported as min, max, median (Q1-Q3) and mean (SD).
IMV (Yes/No) – Within 30 Days	Outcome	HealthVerity	Proportions of patients with IMV (i.e., intubation and MV, extracorporeal membrane oxygenation [ECMO]) usage during the first 30 days of the follow-up period, among patients with any hospitalizations in the follow-up period. IMV will be identified by HCPCS and CPT-4 procedure codes. Reported as counts and percentages.
IMV Usage Duration – Within 30 Days	Outcome	HealthVerity	Number of days of IMV usage during the first 30 days of the follow-up period. Reported as min, max, median (Q1-Q3) and mean (SD).
ICU Admission (Yes/No) – Within 30 Days	Outcome	HealthVerity	Proportions of patients with ICU admission during inpatient admissions during the first 30 days of the follow-up period, among patients with any hospitalizations in the follow-up period. ICU admission will be identified by hospital revenue

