1. COVID-19 reinfection: In the sensitivity analysis, a COVID-19 patient's follow-up period may be further censored at the first COVID-19 reinfection date (if any). The COVID-19 reinfection is defined as another COVID-19 diagnosis at least 90 days of gap after the previous COVID-19 diagnosis. The study measurements among the overall patient population (without stratifications) will be reported for this sensitivity population.

2. **Open-source Cost:** A portion of patients will have claims data that is linked to open-source cost information. A sensitivity analysis of the overall study analysis (not including the stratification analyses) will be carried out among such linked patients. The open-source cost data will be used to represent the cost information in this sensitivity analysis.

Statistical Analysis:

Descriptive Statistics:

Descriptive statistics will be utilized to summarize patient demographic, clinical characteristics, and HCRU and cost outcomes. Counts and percentages will be reported for categorical variables. Continuous variables will be summarized using minimum, maximum, median (Q1-Q3) and mean (SD). The count and percentage of patients with missing data will be reported.

Comparison Statistics:

All study measurements will be compared between the COVID-19 and Control cohorts. Standardized mean differences (SMD) will be reported for all variables.

Regression Analysis:

Multivariable regression analysis will be used to evaluate the potential predictors of long-term HCRU and costs associated with COVID-19.

- 1. The dependent variables of such regression models will include: number of all-cause hospitalizations during the follow-up period, total cost (charge and allowed amount) of all-cause hospitalizations during the follow-up period, number of COVID-19 hospitalizations during the follow-up period, total cost (charge and allowed amount) of COVID-19 hospitalizations during the follow-up period, total cost (charge and allowed amount) of all healthcare claims during the follow-up period, and total cost (charge and allowed amount) of COVID-19-related healthcare claims during the follow-up period.

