Description	Exposur e (aka indepen dent variable)	Covariates	Outcome (aka dependent variable)	Type of regression
COVID-19 hospitalizations during the follow-up period, total cost (charge and allowed amount) of all healthcare claims during the follow-up period, and total cost (charge and allowed amount) of COVID-19- related healthcare claims during the follow-up period		healthcare allowed amount during the baseline period, and index year-month	up period, total cost (charge and allowed amount) of all healthcare claims during the follow-up period, and total cost (charge and allowed amount) of COVID-19-related healthcare claims during the follow-up period	

Inverse Probability of Censoring Weighting (IPCW):

Imbalances in patient characteristics may develop over the follow-up period due to the artificial censoring of patients assigned as controls who later develop COVID-19 or have other censoring events. Inverse probability censored weighting (IPCW) can be used to compensate for such censoring. Therefore, the regression models may also be generated after applying IPCW as described below.^{2,3}

Within each cohort, person-time records will be divided into short intervals depending on computational feasibility (eg, 10 days). Weights will be generated as the inverse of the probability of remaining uncensored at each time, as predicted from Cox regression models using the same baseline patient characteristics employed during matching. Weights will be stabilized by multiplying by the proportion of patients within the cohort who remain uncensored. Among controls, two models will be used: the first for future COVID-19 status and the second for

other censoring events. Stabilized weights from the two models will be multiplied to produce the final weights.

Summaries of the stabilized weights will be presented by cohort. Among patients assigned as COVID-19 cases, SMDs and baseline characteristics will be reported by administrative censoring status during the follow-up period, before and after IPCW. Among patients assigned as controls, SMDs and baseline characteristics before and after IPCW will be reported among those who, during the follow-up period, are: 1) not censored and remain undiagnosed with COVID-19; 2) become censored due to a COVID-19 diagnosis; and 3) become censored due to other events.

Other Statistical Descriptions:

P-value of 0.05 will be used as the threshold to determine the statistical significance of all comparisons and regressions.

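### Aim 3B regresses COVID-19 hospitalizations on a case-versus-control term although controls are zero by design, and its AIC rule cannot choose between a one-part gamma and a two-part cost model

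*SAP*

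**What the plan says.** The SAP for Aim 3B, section 5.6 (Regression Analysis), lists six dependent variables. Three are all-cause. Three are COVID-19-specific: "number of COVID-19 hospitalizations during the follow-up period, total cost (charge and allowed amount) of COVID-19 hospitalizations during the follow-up period", and the cost of COVID-19-related healthcare claims. The summary table gives COVID-19 versus Control as the exposure for all six.

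On how the COVID-19 outcomes are identified, Table 2 (section 5.3) says "COVID-19 hospitalizations are identified by a hospital discharge diagnosis of COVID-19 in any position". It also defines a COVID-19 medical claims cost: "Sum of the costs of all COVID-19-related medical claims, including inpatient and outpatient medical claims during the follow-up period".

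On controls, the matching rules printed under section 5.2.1.2 say "control patients are required to have no COVID-19 diagnoses in any position in any inpatient or outpatient claims prior to 30 November 2022". For a later diagnosis, "the follow-up period of these control patients will be censored at the date of the first inpatient or outpatient claim with a COVID-19 diagnosis". Section 5.2.3 repeats this censoring rule but as something that may happen. Section 5.6, on censoring weights, refers to "the artificial censoring of patients assigned as controls who later develop COVID-19 or have other censoring events".

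Every regression is to give a point estimate and a 95% CI with match-clustered robust standard errors, and "P-value of 0.05 will be used as the threshold to determine the statistical significance of all comparisons and regressions".

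Protocol section 8.7.4 lists the outcome as "COVID-19-related hospitalization (for cases only").

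For costs, section 5.6 makes a gamma model with log transformation the default and uses AIC to compare distributions, and to compare with two-part models for the handling of zeros. Section 5.5 plans on zero costs in 50% of cases and 60% of controls. Protocol section 7 names total healthcare expenditure, COVID-19 against non-COVID-19 patients, as the main summary measure of Aim 3B.

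**The concern.** There are two separate difficulties.

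1. For the two hospitalization outcomes, the claim that would make a control non-zero is the claim that removes the control from follow-up. The model is asked for a case-versus-control ratio whose denominator is fixed at zero by the design.

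2. For the all-cause costs, the rule for choosing the model relies on a likelihood that does not exist at zero, while half or more of the patients are expected to have zero cost. A one-part model gives a ratio over all patients; the positive part of a two-part model gives a ratio among patients with costs. The adjusted result for the aim's main measure could therefore be either, and the stated rule cannot settle which.

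**Working it through.** **The SAP's own figure.** Section 5.5 states power above 0.99. Least favourable stated corner: 50,000 cases, 200,000 controls, zeros 50% and 60%, control mean of non-zero costs $100, ratio 1.15, SD $10,000.
- Zero part: pooled share with costs = (0.50×50,000 + 0.40×200,000)/250,000 = 0.42. z = 0.10/√[0.42×0.58×(1/50,000 + 1/200,000)] = 40.5.
- Positive part: 25,000 and 80,000 patients. z = 15/[10,000×√(1/25,000 + 1/80,000)] = 0.21.
- Two-degree-of-freedom test with noncentrality 40.5² + 0.21²: power 1.0000.

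The stated power reproduces. It assumes that 40% of controls have costs, so it does not describe outcomes where controls are all zero.

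**Part 1, analytically.** A control with count 0 and mean μ contributes −(1/α)·log(1 + αμ) to the negative binomial log-likelihood. This rises as μ falls to 0, so there is no finite maximum for the cohort term. In the gamma estimating equation each control contributes (0 − μ)/μ = −1 whatever μ is, so the equation has no solution. In a two-part model the positive part contains no controls. Censoring weights do not help, because a weighted zero is still zero.

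**Part 1, numerically.** Assumed: 5,000 cases with mean 0.0196, 20,000 controls at zero, negative binomial with dispersion 1.

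| Iterations | Log ratio | Model SE | Log-likelihood |
|---|---|---|---|
| 5 | 7.3 | 1.2 | −484.620 |
| 10 | 12.3 | 14.4 | −484.314 |
| 20 | 22.3 | 2,134 | −484.312 |
| 30 | 32.3 | 316,665 | −484.312 |

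With matched sets and two covariates:
- Stopped at 10 iterations, flagged as not converged: log ratio 12.3, match-clustered SE 0.10.
- Python default stopping rule: log ratio about 26.3, model SE about 14,600 to 16,800, clustered SE from tens to hundreds, or undefined.
- Default R negative binomial fit: reports convergence with log ratio 26.4, model SE 16,091 and an undefined clustered SE.
- One fit forced to 50 iterations printed a clustered SE of 0.28. By then that figure is numerical noise.
- Vaccination coefficient: −0.2370 (SE 0.2279) both with controls and in cases only.

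If censoring-day admissions count, with k of 20,000 controls admitted that day, the ratio is 0.0196/(k/20,000) = 392/k. For k = 1, 5, 20 and 60 this gives 392, 78, 20 and 6.5.

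**Part 2.** The gamma log-density is (k − 1)·log y − y/θ − k·log θ − log Γ(k). At y = 0 it is +∞ for shape 0.5, finite only at shape 1, and −∞ for shape 2. The possible ways round, on 20,000 simulated patients with 60% zeros (two-part AIC 165,365), are:
- Replace zeros by a small amount. One-part minus two-part AIC is −35,343 at $0.01, +58,464 at $1 and +137,233 at $100, so the constant picks the model.
- Drop zeros. AIC 138,403, but only on the patients with costs.
- Fix the shape at 1. In dollars the two-part model wins (165,365 against 308,304); in thousands of dollars the one-part model wins (31,993 against 54,164).
- Solve the gamma equations by quasi-likelihood. This accepts zeros and returns the all-patient ratio, but has no AIC.

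Size of the ambiguity at the planning shares: 1.15 among patients with costs is 1.15×0.50/0.40 = 1.44 over all patients.

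**The case against.** **The third outcome.** It is tempting to say that all three COVID-19-specific outcomes are structurally zero. The documents do not go that far. The regression outcome is COVID-19-related healthcare claims; Table 2 defines only COVID-19 medical claims, and elsewhere in that table all healthcare includes pharmacy. Control exclusion and censoring are triggered by inpatient or outpatient diagnoses, not by dispensing. If pharmacy cost is included, controls can be non-zero. This stands: two outcomes are definite and the third is undefined.

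**Optional censoring.** Section 5.2.3 words the censoring of controls as permissive where the matching rules make it mandatory. If it were optional, controls with later COVID-19 would contribute events and the ratio would be finite. The point stands as a contradiction to reconcile. It does not give a usable contrast, because the result would then depend on who was censored. A diagnosis dated exactly 30 November 2022 is covered by neither rule, which is a minor gap.

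**A falsely significant result.** A reader might infer that an absurd ratio with a narrow CI would be reported as significant. The checks do not support this as the usual outcome: the narrow intervals came from fits stopped before convergence or forced past the normal stopping point, and default fits fail visibly. SAS, which the SAP also allows, was not run.

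**Limited reach.** The stated purpose of the regressions is to evaluate predictors, and the other coefficients are essentially unaffected. The protocol already limits the hospitalization outcome to cases. Part 1 does not touch total expenditure.

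**Part 2 as preference.** The SAP foresees zeros and two-part models, and proposes no added constant. Both are true. But it names AIC as the arbiter, and no route makes that comparison valid. Nor does this discredit AIC generally: it stays valid among full-likelihood models on the same records, including negative binomial against zero-inflated negative binomial.

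**Conclusion.** The concern holds in this form. Under the mandatory censoring rule, the number and cost of COVID-19 hospitalizations have no finite or meaningful case-versus-control ratio, or one set by the censoring-day convention. The same holds for COVID-19-related claims cost only if it means inpatient and outpatient medical claims. The likely consequence is a regression that visibly fails, not a misleading finding. Divergence follows from the design and does not depend on the simulated rates; the particular ratios and standard errors do.

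The AIC comparison of a one-part gamma with a two-part model is invalid with zero costs, leaving open which population the adjusted ratio for the main measure describes. The 1.15 against 1.44 contrast is illustrative, since section 5.5 does not tie its shares to a named cost outcome.

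The all-cause count model, the unadjusted summaries and the power statement are not in question. This should be fixed before the regressions are run.

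**What to change.** 1. Fit the COVID-19-specific outcomes in cases only, without the cohort term, in line with Protocol section 8.7.4.
2. Define COVID-19-related healthcare claims in Table 2 as the inpatient and outpatient COVID-19 medical claims already defined there.
3. Align section 5.2.3 with the mandatory control-censoring rule.
4. For all-cause costs, pre-specify a two-part model, for example logistic plus gamma with log link. Section 5.5 assumes two-part models for power but does not name the parts. Report the combined all-patient mean-cost ratio and difference with match-clustered CIs, for example by bootstrapping matched sets.
5. Limit AIC to full-likelihood models fitted to the same records.

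The cost is SAP wording and standard code, with slightly more programming for the combined CI and no new data. The cases-only models give up only a contrast that the design cannot support.

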Description	Exposur e (aka indepen dent variable)	Covariates	Outcome (aka dependent variable)	Type of regression
COVID-19 hospitalizations during the follow-up period, total cost (charge and allowed amount) of all healthcare claims during the follow-up period, and total cost (charge and allowed amount) of COVID-19- related healthcare claims during the follow-up period		healthcare allowed amount during the baseline period, and index year-month	up period, total cost (charge and allowed amount) of all healthcare claims during the follow-up period, and total cost (charge and allowed amount) of COVID-19-related healthcare claims during the follow-up period	

Inverse Probability of Censoring Weighting (IPCW):

Imbalances in patient characteristics may develop over the follow-up period due to the artificial censoring of patients assigned as controls who later develop COVID-19 or have other censoring events. Inverse probability censored weighting (IPCW) can be used to compensate for such censoring. Therefore, the regression models may also be generated after applying IPCW as described below.^{2,3}

Within each cohort, person-time records will be divided into short intervals depending on computational feasibility (eg, 10 days). Weights will be generated as the inverse of the probability of remaining uncensored at each time, as predicted from Cox regression models using the same baseline patient characteristics employed during matching. Weights will be stabilized by multiplying by the proportion of patients within the cohort who remain uncensored. Among controls, two models will be used: the first for future COVID-19 status and the second for

other censoring events. Stabilized weights from the two models will be multiplied to produce the final weights.

Summaries of the stabilized weights will be presented by cohort. Among patients assigned as COVID-19 cases, SMDs and baseline characteristics will be reported by administrative censoring status during the follow-up period, before and after IPCW. Among patients assigned as controls, SMDs and baseline characteristics before and after IPCW will be reported among those who, during the follow-up period, are: 1) not censored and remain undiagnosed with COVID-19; 2) become censored due to a COVID-19 diagnosis; and 3) become censored due to other events.

Other Statistical Descriptions:

P-value of 0.05 will be used as the threshold to determine the statistical significance of all comparisons and regressions.

All data analyses will be conducted using SAS 9.4 (SAS Institute, Cary, NC) or R (R Foundation, Indianapolis, IN).

